10.3.5.2 Secondary Efficacy Endpoints Analyses

Statistical testing of the 3 key secondary efficacy endpoints will be performed according to the conditional hierarchical testing procedure using the order defined in the objective/endpoints sections. Consequently:

- Efficacy of CVnCoV in regard to moderate and severe cases will be demonstrated only if there is successful demonstration of the primary efficacy objective.
- Efficacy of CVnCoV in regard to severe cases will be demonstrated only if there is successful demonstration of the primary efficacy objective and the key secondary objective on moderate and severe cases.
- Efficacy of CVnCoV in regard to (RT-PCR positive) cases of "wild type" (i.e., WT/D614G lineages A.1/B.1 without VOC B.1.1.7 [Alpha], B.1.351 [Beta], B.1.429 [Epsilon]) and "UK" (B.1.1.7 [Alpha]) will be demonstrated only if there is successful demonstration of the primary efficacy objective and the key secondary objective on moderate and severe cases and severe cases.

Otherwise, these endpoints will be analyzed as exploratory endpoints without success criteria testing.

To assess the efficacy in the prevention of "wild type" (i.e., WT/D614G lineages A.1/B.1 without VOC B.1.1.7 [Alpha], B.1.351 [Beta], B.1.429 [Epsilon]) and "UK" (B.1.1.7 [Alpha]) cases, moderate to severe, severe disease and asymptomatic infections, similar analyses to those performed on the primary efficacy endpoint will be performed. The efficacy will be demonstrated if the lower limit of the exact 2-sided 95% CI of VE is above 30% for "wild type" (i.e., WT/D614G lineages A.1/B.1 without VOC B.1.1.7 [Alpha], B.1.351 [Beta], B.1.429 [Epsilon]) and "UK" (B.1.1.7 [Alpha]) cases, 20% for moderate to severe disease, 10% for severe disease and above 0% for asymptomatic infections.

Other secondary efficacy endpoints will be analyzed similarly to the primary efficacy endpoint but no formal testing will be performed for those endpoints. For efficacy after the first dose, the time to first-occurrence of virologically-confirmed COVID-19 (date of symptom onset) will start after the first vaccination. The BoD will be analyzed using 2 different scoring systems. Both BoD scoring systems place more weight on efficacy against severe COVID-19 or severe disease as reflected by hospitalization or death. In addition, VE and associated CI will be calculated for each of the BoD categories.

10.3.5.3 Exploratory Efficacy Endpoints Analyses

The proportions of COVID-19 cases of any severity caused by identified SARS-CoV-2 VOCs and mild, moderate, and severe COVID-19 cases (according to primary case definition) among all cases will be summarized by group.

Clinical Trial Protocol	CV-NCOV-004
CureVac AG	COVID-19 mRNA Vaccine

Description of frequencies and percentages will be provided by group for subjects who:

- Need supplemental oxygenation due to COVID-19.
- Need mechanical ventilation due to COVID-19.
- Are hospitalized due to COVID-19.
- Died due to COVID-19.
- Died due to any cause.

This will be done for events occurring \geq 15 days following the second trial vaccination (full VE) and then for events occurring at any time after the first trial vaccination.

The VE in the prevention of first episodes of virologically-confirmed cases of COVID-19 of any severity will be reassessed on all subjects whatever their serological status at baseline for cases occurring \geq 15 days following the second trial vaccination and then for all cases occurring after the first dose.

Finally, the number and percentage of subjects who developed a second episode of COVID-19 will be displayed by group.

10.3.6 Secondary and Exploratory Immunogenicity Analysis

No formal hypothesis on immunogenicity will be tested. Descriptive statistics for the immunogenicity endpoints will be provided for each vaccine group and overall, and by vaccine group and age groups. Data will be presented after each vaccine dose.

The following analyses will be performed for antibody levels to the SARS-CoV-2 RBD of S protein and for neutralizing antibodies overall and separately in subjects seronegative at baseline and in subjects seropositive at baseline:

- Geometric mean titers (GMTs) will be summarized with their 95% CI at each blood sampling time point.
- The Fold Change (FC) from baseline will be computed for each subject and Geometric mean of FC (GMFC) will be displayed with their 95% CI at each blood sampling time point after baseline.

Non-detectable antibodies will be arbitrary replaced by half of the detection cut-off for GMT and GMFC computations purpose.

For each readout, the number and percentage of subjects SARS-CoV-2 seronegative at baseline for whom a seroconversion is observed will be summarized and presented at each blood sampling time point after baseline with exact 95% CI. Seroconversion is defined as detectable antibodies in the serum.

Percentages of subjects seroconverting for SARS-CoV-2 RBD of S protein antibodies and SARS-CoV-2 neutralizing antibodies will be summarized. The frequency of immune cell populations induced by the vaccine will be summarized. Further characterization of the T-cell immune response may be done with other technologies like ELISpot, CyTOF and/or analysis of genomic biomarkers.

Additional immunogenicity analyses including graphs will be described in the SAP as applicable.

CV-NCOV-004
COVID-19 mRNA Vaccine

10.3.7 Safety Analysis

Clinical Trial Protocol

CureVac AG

No formal statistical testing of safety data is planned.

The descriptive safety analyses will be performed overall by vaccine group, by age group and vaccine group, and by serostatus and vaccine group.

For the open-label phase, applicable descriptive analyses will also be performed by cohort.

Solicited AEs: The frequencies and percentages of subjects experiencing each solicited local and systemic AE within 7 days after each vaccination will be presented by intensity and overall. For subjects with more than 1 episode of the same AE within 7 days after a vaccination, the maximum intensity will be used for tabulations. Similar tabulations will be performed for solicited systemic AEs by relationship to trial vaccination. Solicited local AEs will be by definition considered as related to the trial vaccine. Time to onset (in days) and duration (in days) will also be summarized for each solicited local and systemic AEs. Summary tables showing the occurrence of at least 1 local or systemic solicited AE within 7 days after each vaccination will also be presented.

Unsolicited AEs: Unsolicited AEs including SAEs and AESIs will be coded using the Medical Dictionary for Regulatory Activities (MedDRA) by System Organ Class (SOC) and Preferred Term (PT).

The frequency and percentage of subjects reporting each unsolicited AE within the 28 days after each vaccination and overall will be tabulated at the SOC and PT levels.

Similar tables will be provided for: related unsolicited AEs, Grade 3 or higher unsolicited AEs, medically-attended AEs that occur within 6 months after the second trial vaccination, SAEs, related SAEs, AESIs, related AESIs, AEs leading to withdrawal or trial discontinuation, and SAEs resulting in death through 1 year after the second trial vaccination.

When an AE occurs more than once for a subject within the 28 days post 1 vaccination, the maximal severity and strongest relationship to the vaccine group will be counted.

Only AE post first vaccination will be considered in the summary tables. AE starting prior to the first vaccination will be recorded as medical history.

Data listings of fatal and SAEs will be provided by subject.

Vital signs will be summarized by descriptive statistics at each visit, including change from baseline, and a listing will be provided.

10.3.8 Interim Analysis

Two interim analyses will be performed for this trial by an unblinded independent statistician and reviewed by the DSMB when 56/111 cases of COVID-19 of any severity (meeting the primary efficacy case definition) are observed. This analysis will aim to assess early high efficacy or futility on the primary efficacy endpoint and will be done on the EAS population only. The safety data that is available at this time point will also be described.

For the analysis of early demonstration of high efficacy or futility, cumulative O'Brien-Fleming type error spending function [36] is used to provide statistical stopping

Clinical Trial Protocol	CV-NCOV-004
CureVac AG	COVID-19 mRNA Vaccine

rules for high efficacy (α -boundaries) and futility (β -boundaries) for the interim analysis, based on the information accumulated until that specific interim stage.

At the interim stage, if the p-value for the test of the primary objective is lower than the α -boundary, a high level of efficacy for CVnCoV will be declared. Conversely, demonstration of futility will occur if the p-value is higher than the β -boundary.

The interim analyses are planned to occur when 56/111 cases of COVID-19 of any severity have been observed. Table 10 below shows the boundaries for demonstrating high efficacy or futility, calculated on a 1-sided p-value scale using the cumulative error spending function. At the time of the interim analysis only descriptive statistics such as the point estimate of VE and respective 95% CI for key secondary objectives will be displayed, no formal testing will be done to protect the overall type one error at the final analyses of 160 cases.

Table 10Two Stage Group Sequential Design with Interim Analyses at 56and 111 Cases and Final Analysis at 160 Cases

	Interim Analysis 1	Interim Analysis 2	Final Analysis
Number of Cases	56	111	160
Efficacy α-Boundary on p-value scale (1-sided)	0.00015	0.00707	0.02281
Futility β-Boundary on p- value scale (1-sided)	0.66345	0.12356	NA
Efficacy success criteria*	Success if ≤ 9 cases in CVnCoV group over 56 cases (observed VE ≥ 80.9%)	Success if ≤ 32 cases in CVnCoV group over 111 cases (observed VE ≥ 59.5%)	Success if ≤ 53 cases in CVnCoV group over 160 cases (observed VE ≥ 50.5%)
Futility*	Futility if ≥ 25 cases in CVnCoV group over 56 cases (observed VE ≤ 19.4%)	Futility if ≥ 40 cases in CVnCoV group over 111 cases (observed VE ≤ 43.7%)	NA

*Rules in terms of split of cases to demonstrate efficacy/futility can slightly differ if the total number of evaluable subjects is unequal in both groups ($r \neq 1$).

If the interim analysis is performed exactly after 56/111 cases have been reported, a 1-sided p-value lower than 0.00015/0.00707 (i.e. lower limit of the 2-sided 99.99/99.3% Cl > 30%) will lead to the conclusion of high efficacy, while a 1-sided p-value higher than 0.66345/0.12356 will result in the demonstration of futility. Otherwise, the final analysis will be performed at 160 cases. Similarly, if the number of evaluable subjects is equal in both groups, it means that the trial will conclude early high efficacy if 9/32 cases or less over 56/111 are coming from the CVnCoV group, while futility of the trial will be demonstrated if 25/40 cases or more are coming from the CVnCoV group.

Of note, the actual boundaries used for decision making would depend on the exact number of cases occurring and reported at each analysis (interim and final).

The boundaries will be applied in a nonbinding way as there are many other factors that would be part of the decision-making process.

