10 STATISTICAL CONSIDERATIONS

10.1 Sample Size Determination

10.1.1 Primary Efficacy Objective

This is an event-driven trial. Sample size and power considerations are based on the primary objective for demonstrating efficacy of CVnCoV in the prevention of virologically-confirmed cases of COVID-19 of any severity meeting the primary case definition. A group sequential design with 2 interim analyses for cases of COVID-19 of any severity demonstrating a high level of efficacy or reaching futility is planned using O'Brien and Fleming type error-spending-function [36] and the sample size is based on the test for one single proportion (i.e. the proportion of cases in the CVnCoV group, among all cases). The group sequential design is based on the any severity COVID-19 endpoint, due to the higher case number required to meet this endpoint.

With an overall 2-sided alpha of 5%, a total of 160 COVID-19 cases of any severity (meeting the primary efficacy case definition for COVID-19 of any severity) are needed at final analysis, to have a power of 90% to demonstrate the VE is above 30% based on the lower bound of the CI for VE, when considering the VE under the alternative hypothesis is 60% (i.e. equivalently to demonstrate the proportion of cases in the CVnCoV group is below 0.4118, based on the upper bound of the CI for proportion when considering the proportion under the alternative hypothesis is equal to 0.2857).

The 2 interim analyses for high efficacy or futility of the primary objective of COVID-19 cases of any severity will be performed once 56/111 cases have been accrued and adjudicated (approximately 30/60% of cases).

Assuming an incidence rate of COVID-19 of 0.15% per month in placebo subjects, an overall non-evaluable rate of 20% (corresponding to subjects excluded from the EAS and drop-outs) and a VE of 60%, 36,500 subjects enrolled over approximately 3 months (18,250 per vaccine group) will accrue 160 COVID-19 cases of any severity at approximately 9 months after the first vaccination. A lower incidence rate, a longer enrollment duration, or a higher non-evaluable rate or VE will delay the acquisition of the 160 cases and the time of final analysis. Subjects will be randomized to receive either CVnCoV or placebo in a 1:1 ratio, stratified by country and age group (18 to 60 and \geq 61 years of age).

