10.3.5 Efficacy Analyses

10.3.5.1 Primary Efficacy Endpoint Analysis

Primary Efficacy Analysis

In primary efficacy analysis, the VE, defined as the percent reduction in the frequency of any COVID-19 cases (according to primary case definitions) in vaccinated subjects

compared with subjects who received placebo will be calculated with exact 95%* CI as follows:

where

ARV = attack rate in vaccinated group = nv/Nv = number of subjects reporting at least 1 COVID-19 episode in the CVnCoV group / total follow-up time of evaluable subjects in the CVnCoV group (number of person-month).

ARP = attack rate in placebo group = np/Np = number of subjects reporting at least 1 COVID-19 episode in the placebo group / total follow-up time of evaluable subjects in the placebo group (number of person-month).

RR = relative risk = ARV/ARP

p = proportion of COVID-19 cases (according to primary case definition) coming from the CVnCoV group among all cases = nv/(nv+np).

r = ratio of total follow-up time of evaluable subjects in the CVnCoV group over total follow-up time of evaluable subjects in the placebo group = Nv/Np.

*Level of CI may be slightly adjusted due to the sequential design (see Section 10.3.8).

The statistical hypotheses for the primary efficacy endpoint is:

 H_{0A} : VE $\leq 30\%$ versus H_{1A} : VE > 30%

A is related to COVID-19 cases of any severity

The trial will be successful if either the lower limit of the exact 2-sided 95% (to be slightly adjusted to consider the sequential design) CI of VE endpoint is > 30% for all COVID-19 cases of any severity or if the lower limit of the exact 2-sided 95% CI of VE endpoint is > 20% for severe to moderate COVID-19 cases.

If the 2 interim analyses and the final analysis for COVID-19 cases of any severity are performed after 56/111 and 160 cases have been reported, respectively, the 1-sided α -risk to consider at the time of final analysis according to O'Brien-Fleming type error spending function will be 0.02281 and efficacy will be demonstrated at the final analysis if 53 cases or less over 160 are in the CVnCoV group (observed VE \geq 50.5%). To note, the rule in terms of split of cases to demonstrate efficacy can slightly differ if r \neq 1 (total follow-up time different in both groups).

Sensitivity Analysis

As a key sensitivity analysis, the time to first-occurrence of virologically-confirmed COVID-19 cases (according to primary case definitions) will be analyzed.

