11.0 Interim Analyses

Two interim analyses are performed for this trial by an unblinded independent statistician with no previous involvement in the trial and reviewed by the DSMB when 56 and 111 cases of COVID-19 (meeting the primary efficacy case definition) are observed. These analyses aim to assess early high efficacy or futility on the primary efficacy endpoint of COVID-19 cases of any severity and are done on the EAS only. The safety data that is available at this time point is be described.

For the analysis of early demonstration of high efficacy or futility, cumulative O’Brien-Fleming type error-spending-function [1] is used to provide statistical stopping rules for high efficacy (α -boundaries) and futility (β -boundaries) for the interim analyses, based on the information accumulated until that specific interim stage.

At the interim stage, if the p-value for the test of the primary endpoint of COVID-19 cases of any severity is lower than the α -boundary, a high level of efficacy for CVnCoV is declared. Conversely, demonstration of futility occurs if the p-value is higher than the β -boundary.

The interim analyses are planned to occur when 56 and 111 cases of any severity, meeting the primary case definition have been observed. The analysis of this primary endpoint is performed as described in detail in Section 12.6.1 and Section 12.6.2.1. If the interim analyses are performed exactly after 56/111 cases have been reported, a 1-sided p-value lower than 0.00015/0.00707 (i.e. LL of the 2-sided

99.97%/98.586% CI > 30%) for the test on the primary endpoint of COVID-19 cases of any severity leads to the conclusion of high efficacy, while a 1-sided p-value higher than 0.66345/0.12356 results in the demonstration of futility. Otherwise, the final primary efficacy analysis is performed at 160 cases.

Table 12 below shows the boundaries for demonstrating high efficacy or futility based on 56 and 111 cases, calculated on a one-sided p-value scale using the cumulative error spending function.

Table 12: Decision rules for interim and final analyses based on 56, 111 and 160 cases

	Interim Analysis 1	Interim Analysis 2	Final Analysis
Number of cases	56	111	160
Efficacy α -Boundary on p-value scale (1-sided)	0.00015	0.00707	0.02281
Futility β -Boundary on p-value scale (1-sided)	0.66345	0.12356	NA

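### The protocol's interim success rule prints two-sided CI levels of 99.99%/99.3% where its own p-value boundaries require 99.97%/98.586%

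*Protocol*

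**What the plan says.** Protocol Section 10.3.8 states the interim efficacy rule in three forms and presents them as the same rule:

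- **p-value:** "a 1-sided p-value lower than 0.00015/0.00707" leads to a conclusion of high efficacy. Table 10 gives the same boundaries.
- **Confidence interval:** introduced by an i.e., "lower limit of the 2-sided 99.99/99.3% Cl > 30" per cent.
- **Case split, equal numbers of evaluable subjects:** "the trial will conclude early high efficacy if 9/32 cases or less over 56/111 are coming from the CVnCoV group". Table 10 gives the same splits.

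SAP Section 11.0 has the same p-value boundaries but different interval levels: "99.97%/98.586% CI > 30" per cent. For the final analysis, SAP Section 12.6.2.1 pairs a one-sided level of 2.281% with an exact two-sided 95.438% Clopper-Pearson interval.

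**The concern.** A one-sided test at level α rejects exactly when the relevant limit of the two-sided 1 − 2α interval clears the null value. The protocol labels its intervals two-sided but does not double α. One paragraph therefore gives a p-value rule and an interval rule that are called equivalent and are not, and the protocol and SAP give different interval thresholds for the same decision.

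Read literally, a result exactly on the stated case limit would be high efficacy by p-value and case count but not by confidence interval. Anyone who takes the interim rule for the trial report from this paragraph would carry the wrong levels forward.

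**Working it through.** **Inputs**

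- Overall two-sided α of 5% and the final case count: "With an overall 2-sided alpha of 5%, a total of 160 COVID-19 cases of any severity" (Protocol 10.1.1).
- O'Brien-Fleming type spending and a single-proportion test: "Fleming type error-spending-function [36] and the sample size is based on the test for one single proportion" (Protocol 10.1.1).
- Null proportion: VE = 30% with equal follow-up (r = 1) gives p0 = 0.7/1.7 = 0.4118, as in "to demonstrate the proportion of cases in the CVnCoV group is below 0.4118".
- Final rule: the one-sided boundary "will be 0.02281 and efficacy will be demonstrated at the final analysis if 53 cases or less over 160 are in the CVnCoV group" (Protocol 10.3.5.1).
- Interval type: Clopper-Pearson for p, converted by VE lower limit = 1 − UL/[(1 − UL)·r], here with r = 1 (SAP 12.6.2.1).

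**Step 1. Reproduce the p-value boundaries.** O'Brien-Fleming type spending of one-sided 0.025 at information fractions 56/160, 111/160 and 160/160 gives 0.000151, 0.00707 and 0.02281. These match Table 10.

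**Step 2. Reproduce the case splits.** Exact lower-tail binomial probabilities at p0:

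| Cases in CVnCoV group | One-sided p | Boundary | Success? |
|---|---|---|---|
| 9/56 | 0.000051 | 0.00015 | yes |
| 10/56 | 0.000176 | 0.00015 | no |
| 32/111 | 0.00478 | 0.00707 | yes |
| 33/111 | 0.00843 | 0.00707 | no |
| 53/160 | 0.0224 | 0.02281 | yes |
| 54/160 | 0.0327 | 0.02281 | no |

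The limits of 9, 32 and 53 are confirmed.

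**Step 3. Convert the boundaries to two-sided levels.**

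- 1 − 2 × 0.00015 = 99.97%
- 1 − 2 × 0.00707 = 98.586%
- 1 − 2 × 0.02281 = 95.438%

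All three agree with the SAP. The protocol's interim levels come from 1 − 0.00015 = 99.985%, rounded to 99.99%, and 1 − 0.00707 = 99.293%, rounded to 99.3%. As two-sided levels, the printed figures imply one-sided α of 0.00005 and 0.0035, about one third and one half of the stated boundaries.

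**Step 4. Apply both sets of levels to the stated case limits.**

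| Cases | Level | Upper limit for p | VE lower limit | Above 30%? |
|---|---|---|---|---|
| 9/56 | 99.99% (protocol) | 0.4122 | 29.9% | no |
| 8/56 | 99.99% (protocol) | 0.3900 | 36.1% | yes |
| 9/56 | 99.97% (SAP) | 0.3931 | 35.2% | yes |
| 10/56 | 99.97% (SAP) | 0.4147 | 29.2% | no |
| 32/111 | 99.3% (protocol) | 0.4168 | 28.5% | no |
| 31/111 | 99.3% (protocol) | 0.4072 | 31.3% | yes |
| 32/111 | 98.586% (SAP) | 0.4052 | 31.9% | yes |
| 33/111 | 98.586% (SAP) | 0.4148 | 29.1% | no |

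The SAP levels return exactly 9/56 and 32/111. The protocol levels return 8/56 and 31/111, one case stricter at each interim.

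**Step 5. Size of the difference.** At a true VE of 60%, p = 0.4/1.4 = 0.2857. The binomial probability of being at or below the limit is:

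- Interim 1: P(X ≤ 9) = 2.3%; P(X ≤ 8) = 1.0%.
- Interim 2: P(X ≤ 32) = 57%; P(X ≤ 31) = 49%.

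Across all three looks, ignoring futility, limits of 8/31/53 instead of 9/32/53 change one-sided type I error from 2.36% to 2.29% and power from 91.4% to 91.3%.

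**The case against.** The arithmetic is not in dispute; the objections concern weight.

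- **The interval is a gloss.** Section 10.3.8 defines the decision by p-value, and its boundaries and case splits are right. The SAP carries the right levels, and its change history records a correction to the first-interim CI in version 3.0 of 27 May 2021. This stands, and it shows which figure to keep. It does not make the protocol's parenthesis correct.
- **The first-interim conflict depends on rounding.** At the unrounded 99.985%, 9/56 gives a VE lower limit of 31.9% and passes; only the printed 99.99% makes it fail, by about 0.1 percentage point. This stands. The second-interim conflict does not depend on rounding: 32/111 gives 28.6% at 99.293% and 28.5% at 99.3%.
- **The 57% to 49% change is not lost power.** It is the chance of meeting the limit at that look. A trial that misses there can continue to 160 cases, and overall power changes by only about 0.1 percentage point. This also stands.
- **No decision now depends on it.** The boundaries are non-binding and are re-derived at the actual case counts, the printed levels err on the strict side, and Protocol Section 3.1.4 already reports the final efficacy analysis on 228 cases. Nothing in the documents shows that the wrong levels were used for a decision. This limits the consequence to the accuracy of the record.

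**Conclusion.** The point holds. The two-sided levels in Protocol Section 10.3.8 are wrong and contradict the p-value boundaries and case splits beside them, Table 10, and SAP Section 11.0. The correct levels are 99.97% and 98.586%.

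Taken literally, the printed levels tighten each interim limit by one case. This markedly lowers the chance of early success at the second look but leaves overall error rates almost unchanged and does not inflate type I error. The case counts assume equal follow-up (r = 1), planned looks at exactly 56 and 111 cases, and Clopper-Pearson limits as the SAP specifies. The level conversion itself needs none of these assumptions.

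**What to change.** In Protocol Section 10.3.8, replace 99.99/99.3% with 99.97/98.586%, as in SAP Section 11.0. If the protocol will not be amended again, state the correction in a short note in the clinical trial report where the interim rules are described. The cost is one phrase; no boundary, case limit or analysis changes.
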